| 
 • Date of last actual dose of randomized study treatment from the IP Discontinuation eCRF form. 
 ○ The dose steps used by the dosing algorithm described in the protocol include a dose hold or a zero dose. If participants are assigned by the algorithm to a zero dose, they do not receive randomized treatment for that period. Hence, it would be possible for a participant to complete the study, while still following the dosing algorithm, but not actually taking any actual randomized treatment. The last non-zero dose date then captures the latest date in the study that a participant physically took a dose of randomized treatment. • The eCRF allows for the possibility of partial or missing dates to be recorded for the last actual dose of randomized study treatment on the IP Discontinuation form (i.e., missing day, or day and month, or day and month and year). In such a case, or in case of a missing IP Discontinuation form, the following conventions will be applied in order to impute a last non-zero dose date: 
 ○ Missing day: 
 ▪ The last day of the month will be used, unless the treatment stop date also occurs in the same month; in this case, the treatment stop date will be used. ○ Missing day and month; 
 ▪ ‘31’ will be used for the day and ‘Dec’ will be used for the month, unless the treatment stop date also occurs in the same year; in this case the treatment stop date will be used. ○ Missing day, month, and year: 
 ▪ Treatment stop date will be used only for participants who have a non-missing treatment start date. |

CONFIDENTIAL

205270

| |
|---|
| General |
| Treatment Stop Date |
| 
 Calculated as the latest randomized treatment dose stop date. The eCRF does not allow for the possibility of missing or partial dates to be recorded for the dose stop date on the study treatment form |
| End of Treatment Value |

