| 
 • The calculation of the average monthly oral iron from Randomization to Week 28 will follow the calculation of the average monthly IV iron from Randomization to Week 28 in Section 10.6.3 below. |
| Average Monthly Oral Iron from Week 24 to Week 28 |
| 
 • The calculation of the average monthly oral iron from Week 24 to Week 28 will follow the calculation of the average monthly IV iron from randomization to Week 28 in Section 10.6.3 below, except randomization date will be replaced with Week 24 date. |
| Reduction in Oral Iron Supplementation |
| 
 • A reduction in Oral iron supplementation relative to baseline occurs when Baseline average monthly oral |

CONFIDENTIAL

205270

| Iron Endpoints | | | | | | | | | | | | | | | | | | | | | | | | | | | | | | | | | | | | | | | | | | |
|---|--|--|-------------------|------------------|---|----------|------------------|---|-----------|------------------|---|----------|------------------|---|---------|-----|----|--------|------------|---|--------|---------------|-----------|-----|----------------|----|--------|---------------|-----|---------|---------------|------|---------|--------------|------|---------|-------------|---|--------|-----|----|--------|
| iron > EP average monthly oral iron, when both baseline oral iron and EP average monthly oral iron are non-missing. | | | | | | | | | | | | | | | | | | | | | | | | | | | | | | | | | | | | | | | | | | |
| Baseline Average Monthly IV Iron | | | | | | | | | | | | | | | | | | | | | | | | | | | | | | | | | | | | | | | | | | |
| 
 Participants may receive up to one IV iron dose within the 8 weeks prior to screening and no IV iron use between screening visit and randomization (Day 1) If no IV iron was used within the 8 weeks prior to screening, the baseline monthly IV iron dose is 0; otherwise the recorded one IV iron dose is the baseline monthly IV iron dose. | | | | | | | | | | | | | | | | | | | | | | | | | | | | | | | | | | | | | | | | | | |
| Average monthly IV iron from Randomization to Week 28 | | | | | | | | | | | | | | | | | | | | | | | | | | | | | | | | | | | | | | | | | | |

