| 
 In order to calculate the average monthly IV iron dose from Randomization to Week 28, the dose of IV iron will be standardized to obtain a continuous single unit IV iron dose in terms of mg/month for the period from the Randomization date to the Week 28 visit date while the subject is on treatment. 
 Note: Participants who are randomized but never treated will not have a value for average monthly IV iron from Randomization to Week 28. The time period starts with treatment start date, instead of randomization date. [missing treatment start date are excluded] If the treatment end date [non-zero dose] is prior to the Week 28 date, then that is used instead. The last non-zero dose date is used for Dapro, treatment end date used for Placebo. IV iron therapy concomitant medication records that occur or are ongoing during the period from the participant's Day 1 visit date to the Week 28 visit date will be selected and ordered by start date and end date. The standardization will be carried out with the following formula: 
 Standardized IV iron dose (mg/week) = IV iron drug dose (mg) * frequency | | | | | | | | | | | | | | | | | | | | | | | | | | | | | | | | | | | | | | | | | | |
| Note: Frequency and Gap Factors defined as follows: | | | | | | | | | | | | | | | | | | | | | | | | | | | | | | | | | | | | | | | | | | |

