| Every 12 Hours | 14 | 0 days | | | | | | | | | | | | | | | | | | | | | | | | | | | | | | | | | | | | | | | | |
| Every 2 weeks | 0.5 | 13 days | | | | | | | | | | | | | | | | | | | | | | | | | | | | | | | | | | | | | | | | |
| Every 4 weeks | 0.25 | 27 days | | | | | | | | | | | | | | | | | | | | | | | | | | | | | | | | | | | | | | | | |
| Once a month | 0.23 | 29 days | | | | | | | | | | | | | | | | | | | | | | | | | | | | | | | | | | | | | | | | |
| Once a week | 1 | 6 days | | | | | | | | | | | | | | | | | | | | | | | | | | | | | | | | | | | | | | | | |
| TID | 21 | 0 days | | | | | | | | | | | | | | | | | | | | | | | | | | | | | | | | | | | | | | | | |
| 
 If the frequency of the record is not 'one time dose', then duration is calculated as follows: 
 If the concomitant medication record start date \geq Randomization date, the duration of the record is 0. If the concomitant medication record end date + gap factor < (Randomization date), the | | | | | | | | | | | | | | | | | | | | | | | | | | | | | | | | | | | | | | | | | | |

CONFIDENTIAL

205270

Iron Endpoints

- duration of the record is 0.
- If the concomitant medication record end date + gap factor \geq (Randomization date) or the record is ongoing, the duration of the record will be calculated as Stop Date – Start Date +1 day where:
 - Start date will be the latest of (concomitant medication record start date and the Randomization date).
 - Stop date will be the earliest of (concomitant medication record stop date + gap factor and the day before randomization).
- If the frequency of the record is 'one time dose', then:
 - If concomitant medication record start date < Randomization date, or if Randomization date \leq concomitant medication record start date, then duration of the record is 0.
 - If Randomization date \leq concomitant medication record start date < Randomization date, then:
 - Frequency (for standardization formula) = 1
 - Duration = 7 days
- The total dose for each IV iron record will be: Standardized dose*duration/7 days
- A weighted mean will then be used to obtain the baseline monthly IV iron dose:
 Mean baseline monthly IV iron dose = [(IV iron total dose_{Record 1}) + ... + (IV iron total dose_{Record n})]/[(16* 7)/30.4375 days].

Blood Pressure Endpoints**BP Exacerbation**

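### SAP 10.6.3 gives every on-study iron record a duration of zero and divides by 16 weeks, in conflict with the workable formula in SAP 7.4.2

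*SAP*

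**What the plan says.** SAP 10.6.3 (Iron Endpoints) describes an on-treatment average of IV iron between randomization and Week 28. Notes under that heading add "The time period starts with treatment start date, instead of randomization date" and, for the end of the window, "The last non-zero dose date is used for Dapro, treatment end date used for Placebo".

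Each record contributes its weekly dose times duration/7. Durations are set as follows:

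- **Repeat-dose record:** zero if it starts on or after randomization, and zero if its end plus the gap factor falls before randomization. Otherwise "Start date will be the latest of (concomitant medication record start date and the Randomization date" and "Stop date will be the earliest of (concomitant medication record stop date + gap factor and the day before randomization".
- **One-time dose:** zero if dated before randomization or dated on or after it; 7 days if dated on or after randomization and also before it.

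Then "A weighted mean will then be used to obtain the baseline monthly IV iron dose": the summed dose is divided by (16 × 7)/30.4375.

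Oral iron to Week 28 follows the same calculation. Oral iron over Weeks 24 to 28 does too, "except randomization date will be replaced with Week 24 date". A participant has reduced oral iron when the baseline monthly oral "iron > EP average monthly oral iron, when both baseline oral iron and EP average monthly oral iron are non-missing".

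SAP 7.4.2 (Iron Parameters) defines the averages to Week 28 differently: on-treatment elemental iron in mg, divided by treatment days/30.4375. It cross-refers to 10.6.3. It also plans a count of reductions both for the evaluation period (EP, Table 2.103) and for the treatment period (Table 2.104).

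The baselines have their own definitions: a 4-week total for oral iron (SAP 10.6.3) and an 8-week pre-screening total for IV iron (SAP 5.2.1).

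**The concern.** The 10.6.3 heading is post-randomization, but its date limits, its label and its divisor are those of a pre-randomization window. A programmer who follows the detailed appendix gets no on-study iron at all. One who follows 7.4.2 gets sensible averages for Tables 2.102 and 2.105, but has no written alternative for the EP oral average behind Table 2.103.

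All-zero averages would probably be seen at the dry run, which covers these tables (SAP 10.10.3 and 10.10.6). The divisor is harder to spot: with corrected dates it produces plausible non-zero numbers that are wrong.

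There are three smaller problems:

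- **Treatment-period reduction.** Table 2.104 has no matching rule, because reduction is defined only against the EP average.
- **End date by arm.** SAP 10.6.1 says of dose holds that "If participants are assigned by the algorithm to a zero dose, they do not receive randomized treatment for that period". A zero-dose period at the end of treatment therefore shortens the window in the daprodustat arm only.
- **Month scaling.** The reduction rule compares a 28-day baseline total with a rate per 30.4375 days.

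**Working it through.** **1. Durations.** Let R be the reference date, used consistently, with duration = stop − start + 1.

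| Record | Rule in SAP 10.6.3 | Duration |
|---|---|---|
| Repeat, start ≥ R | set to zero | 0 |
| Repeat, end + gap < R | set to zero | 0 |
| Repeat, spanning R or ongoing at R | start = R, stop = R − 1 | (R − 1) − R + 1 = 0 |
| One-time, start < R or start ≥ R | set to zero; covers every date | 0 |
| One-time, 7-day branch | needs R ≤ start < R | never met |

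The gap factor drops out because the stop date is capped at R − 1. As a check, 588,060 repeat-dose records were enumerated for each R: starts from day −120 to 239, ends up to day 239 or ongoing, and the nine distinct gap factors in the SAP. With R at randomization, at a later treatment start (1 or 7 days later) or at Week 24 (day 168), every duration was 0. One-time doses also gave 0 throughout.

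If only the named date is replaced for Week 24, and the cap stays at the day before randomization, a record spanning Week 24 gets −1 − 168 + 1 = −168 days. No reading gives a positive duration.

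**2. Effect on the reduction flag.** With an EP average of zero (or negative), baseline > EP holds for anyone with positive baseline oral iron, including a participant on a constant dose.

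**3. Divisor.**

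- SAP 10.6.3: 112/30.4375 = 3.680 months
- 28 weeks on treatment: 196/30.4375 = 6.439 months
- 4-week EP: 28/30.4375 = 0.920 months

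Sixteen weeks matches none of the iron windows in the SAP: 4-week oral baseline, 8-week IV baseline, 28-week treatment period, 4-week EP.

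**4. If the dates are repaired and the divisor is kept** (illustrative doses):

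- One 1000 mg IV dose over 28 weeks on treatment: 1000/3.680 = 271.8 mg/month, against 1000/6.439 = 155.3 under 7.4.2. The ratio is 28/16 = 1.75.
- Constant oral dose of D mg/day in a 4-week EP: 28D/3.680 = 7.6D, against 28D/0.920 = 30.4D on the correct scale. The ratio is 4/16 = 0.25. Baseline is 28D, so 28D > 7.6D and the participant is flagged. With an EP daily dose D′, escaping the flag needs 28D′/3.680 ≥ 28D, that is D′/D ≥ 3.68.

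**5. After full repair, without rescaling baseline.** The flag needs 28D > 30.4375D′, or D′/D < 0.920. A true cut of up to 8.0% is missed.

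**The case against.** The strongest reply is that the plan also contains a usable rule. SAP 7.4.2 gives a complete formula for Tables 2.102 and 2.105, and the opening notes in 10.6.3 state a sensible window start. That is true, but 7.4.2 sends the reader to 10.6.3 for detail and no order of precedence is given. For the EP oral average the 7.4.2 formula could be extended by analogy, but the only derivation actually written is the defective one.

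Other points narrow the finding without removing it:

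- Baseline oral and IV iron are defined separately and are not zeroed. The problem concerns records put through the on-treatment calculation.
- The Week 24 result of zero assumes that every reference to randomization is replaced. The narrower substitution gives negative durations, and the Table 2.103 flag is just as wrong.
- The 1.75 and 3.68 figures depend on a partial repair that nobody has proposed. The 1.75 applies to a full 28 weeks: for shorter exposure the ratio is weeks on treatment/16, which is 1 at 16 weeks and below 1 earlier.
- The 8% scaling effect is a refinement. The baseline IV figure is a larger mismatch: an 8-week total, or 56/30.4375 = 1.84 months, shown as a monthly dose. It should be corrected at the same time.
- The frequency of terminal dose holds is not given, so the effect of the arm-specific end date cannot be sized.

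**Conclusion.** The concern holds and is minor. As written, the on-treatment iron calculation in 10.6.3 cannot give a positive duration, its label and divisor contradict its heading, and it conflicts with 7.4.2. The zero follows from the printed limits and needs no assumption about the data beyond using one reference date consistently; otherwise the result is zero or negative. The sizes quoted for a partial repair assume 28 weeks on treatment or a 4-week EP, with illustrative doses.

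The affected displays are Tables 2.102 to 2.105. They are descriptive, since SAP 7.4 plans no testing of exploratory endpoints. The primary and principal secondary analyses do not use these quantities.

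**What to change.** Amend SAP 10.6.3 as follows:

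1. State that the 7.4.2 formula governs. Remove the baseline label and the 16-week divisor.
2. Define the window as treatment start (or the Week 24 visit for the EP) to the earlier of the Week 28 visit and treatment stop, with the same end-date rule in both arms.
3. For each repeat-dose record, start at the later of record start and window start, and stop at the earlier of record stop plus gap factor and window end. Ongoing records stop at window end; records with no overlap contribute zero. A one-time dose counts in full if dated within the window.
4. Divide total mg by (window days/30.4375). As a test case, a constant 100 mg/day should give 3043.75 mg/month over both the 28-week and the EP window.
5. Put baseline oral iron on the same 30.4375-day scale before applying the reduction flag, and do the same for baseline IV iron where it is shown beside the on-treatment average.
6. Define the reduction flag for the treatment period (Table 2.104) as well as for the EP (Table 2.103).

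The cost is appendix wording and derivation code. No new data are needed.

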7.1.4. Strategy for Intercurrent (Post-Randomization) Events

The following are the intercurrent events for the primary efficacy analyses:

- Death prior to the end of the EP (i.e. before Week 28 visit)
- Randomized treatment discontinuation prior to the end of the EP
- Use of non-randomized ESA medications for any reason including rescue prior to the end of the EP
- Receipt of blood transfusions prior to the end of the EP

Except for the intercurrent event of deaths prior to the end of the EP, a treatment policy strategy will be used in which all scheduled Hgb data recorded during the EP (Weeks 24-28) will be included in the primary efficacy analysis, regardless of discontinuation of study medication due to any reasons, and regardless of receipt of non-randomized ESA medications for any reason including rescue, or blood transfusions. For deaths, a hypothetical strategy will be used as described in Section [7.1.5.1](#).

The following are causes of missing Hgb data affecting the primary efficacy endpoint that are not due to intercurrent events:

- Study withdrawal prior to the end of the EP
- Permanent switching from clinic visits to remote visits prior to start to EP
- Intermittent missing Hgb values at one or more visits with the EP

Missing data will be imputed as described in Section 7.1.5.1.

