7.1.5.1. Statistical Methodology Specification

| |
|---|
| Endpoint / Variables |
| 
 • Mean change in Hgb between baseline and over the evaluation period (EP, mean over Weeks 24 to 28) |
| Model Specification |
| 
 • The EP Hgb value will be defined as the mean of all available Hgb values (on and off-treatment) during the EP (Week 24 to Week 28 inclusive) • The ANCOVA model used to quantify the difference in mean Hgb change will adjust for the following baseline values: 
 ○ Treatment ○ Baseline Hgb (see Section 5.2) ○ Region (as randomized, see Section 5.3 & Section 5.4) |
| Multiple Imputation Analysis |
| 
 • Multiple imputation analysis will be performed using all available Hgb values (on and off-treatment) and conducted under a set of assumptions about missing Hgb values (see Section 10.6.3). 
 ○ For each of the missing dataset (out of the 200 imputed as indicated above), the missing scheduled Hgb values through Week 28 will be imputed based on the MNAR assumption and will be performed using PROC MI. The regression will have region, treatment, baseline Hgb, off treatment status, prior scheduled (possibly imputed) Hgb values as covariates (see Model Checking & Diagnostics, below). The seed for reproducibility is set to 205270. ○ Missing data will be considered MNAR and classified as either being on-treatment or off-treatment, with the former being imputed with only on-treatment data and the latter being imputed with only off-treatment data 
 ▪ Subsequent missing data will be classified as being on-treatment, if 
 • Patients who die, use non-randomized ESA Medication, Receipt of Blood Transfusions while on treatment • Study Drug Interruption (e.g. temporarily stopped trt due to COVID, then restarted) ▪ Subsequent missing data will be classified as being off-treatment, if 
 • Treatment discontinuation • Patients who die, use non-randomized ESA Medication, Receipt of Blood Transfusions after treatment discontinuation |

CONFIDENTIAL

205270

- The low and high cutoffs at Hgb values of 6 g/dL and 15 g/dL will be applied to all imputed Hgb values.

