- EP Hgb values will be computed and compared across treatment groups using the co-primary ANCOVA model described above. Rubin's rules [Rubin, 1987] will be used to combine results of the imputed datasets using SAS PROC MIANALYZE procedure. As a result, a single estimated treatment difference and its standard error will be produced, with which a 95% CI will be calculated.

Model Checking & Diagnostics

- Distributional assumptions underlying the model used for analysis will be examined by obtaining a normal probability plot of the residuals and a plot of the residuals versus the fitted values (i.e. checking the normality assumption and constant variance assumption of the model respectively) to gain confidence that the model assumptions are reasonable.
- If there are any departures from the distributional assumptions, alternative models will be explored using appropriate transformed data.
- Models will be examined for treatment interactions with baseline Hgb and stratification factor
- Missing data imputation:
 - When imputing for each of the missing dataset (out of the 200), if there are error and or warning messages related to the by statement and/or regression model (e.g. not enough observations with the statement), try impute with randomized treatment, baseline Hgb, treatment status, prior scheduled (possibly imputed) Hgb values and region as covariates.
 - If there are no observed off-treatment Hgb values at a visit, the missing Hgb values at that visit will be imputed based on only the observed on-treatment Hgb values.

Model Results Presentation

- All available observed Hgb values (on and off-treatment) will be summarized using mean, standard deviation, minimum, P25, median, P75 and maximum at each visit by treatment group. In addition to scheduled visits, the baseline value and mean EP will be included (see Section 10.6.3). The summaries described above will be produced using the analysis defined Hgb.
 - This display will be repeated for visits up to and including Week 28, using the data used for the primary Hgb analysis (i.e., including imputed values).
- All available observed Hgb change from baseline values (on and off-treatment) will also be summarized using mean, standard deviation, minimum, P25, median, P75, and maximum at each post-baseline visit, including the mean EP (see Section 10.6.3).

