10.4.1.1. Treatment States for Hgb, Iron Parameters, Transfusion and PRO Data

| Treatment State | Definition |
|-----------------|--|
| Pre-Treatment | Date \leq Treatment Start Date |
| On-Treatment | Treatment Start Date < Date \leq Treatment Stop Date + 1 day |
| Post-Treatment | Date > Treatment Stop Date + 1 day |

NOTES:

- If the treatment stop date is missing and the treatment start date is non-missing, then the assessment will be considered to be On-Treatment

10.4.1.2. Treatment States for BP, Lipid Parameters, Clinical Chemistry, Hematology, Other Laboratory Tests, Hepatobiliary (Liver) and Vital Signs Data

| Treatment State | Definition |
|-----------------|--|
| Pre-Treatment | Date \leq Treatment Start Date |
| On-Treatment | Treatment Start Date < Date \leq Last Non-Zero Dose Date + 1 day |
| Post-Treatment | Date > Last Non-Zero Dose Date + 1 day |

NOTES:

- If the treatment stop date is missing and the treatment start date is non-missing, then the assessment will be considered to be On-Treatment

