10.6.2. Study Population

| |
|--|
| Demographics |
| Age |
| 
 Only year of birth will be collected in this study for privacy protection reasons. The day and month of the DOB will not be collected for any site. GSK standard IDSL algorithms will be used for calculating age where birth month and date will be set to “30th June.” Birth date will be presented in listings as ‘YYYY’. |

CONFIDENTIAL

205270

| |
|---|
| Demographics |
| Body Mass Index (BMI) |
| 
 Calculated as $\text{Weight (kg)} / [\text{Height (m)}]^2$ |
| Race Groups |
| 
 Geographic ancestry data will be combined into categories as provided by the United States (US) Food and Drug Administration (FDA) and summarized as FDA race group: 
 American Indian or Alaskan Native Asian (Asian-East Asian Heritage, Asian-Japanese Heritage, Asian-Central/South Asian Heritage, Asian-South East Asian Heritage, Asian-Mixed Race) Black (African American/African Heritage) Native Hawaiian or Other Pacific Islander White (White-Arabic/North African Heritage, White-White/Caucasian/European Heritage, White – Mixed Race) Mixed Race (Multiple races are selected, but excludes Asian – Mixed Race and White – Mixed Race) 
Note: Asian – Mixed Race includes participants who have more than one Asian category selected, but no other categories. White – Mixed Race includes participants who have more than one White category selected, but no other categories.
 |

| |
|--|
| Randomized Treatment Discontinuation, Study Withdrawal, and Possible Follow-up Time |
| Randomized Treatment Discontinuation |
| 
 Randomized Treatment Discontinuation Censored Time (days) = Treatment stop date – Randomization date +1 
Note: In the case where a participant on randomized treatment is lost to follow-up, a final treatment stop date is presumed, though unobserved. In this case, the last point of contact of the participant is used for both the treatment stop date and withdrawal date.
 
In the case where a participant on randomized treatment dies and has a missing treatment stop date, the date of death or imputed date of death (see Section 10.7.2.1) will be used for the treatment stop date.
 |
| 
 Time to Randomized Treatment Discontinuation (days) = Treatment stop date – Randomization date +1 |

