| 
 ● Generate missing rows for subjects who are missing any scheduled visits 
 ○ Baseline does not need to be generated since a subject must have a baseline HGB to be randomized ● Populate variable "DTYPE" with "IMPUTED" for subjects with these newly created missing rows ● For date "ADT", anchor on the baseline visit date, then add the subsequent weeks needed 
 ○ For example of week 2 is missing then ADT = baseline ADT + 2 weeks ● For "APHASE", deciding if the missing row should be marked as "On-Treatment" or "Post-Treatment", the generated ADT should be compared to treatment end date "TRTEDT". If $TRTEDT + 1 \geq ADT$ then "On-Treatment" or if $TRTEDT + 1 < ADT$ then "Post-Treatment". |
| SF-36 |
| 
 ● Generate missing rows for subjects who are missing baseline, week 8, week 12, and week 28 sf-36 vitality scores (norm and traditional) ● Populate variable "DTYPE" with "IMPUTED" for subjects with these newly created missing rows ● For date "ADT", anchor on the baseline visit date, then add the subsequent weeks needed 
 ○ If the baseline (Day 1) is missing then baseline ADT will be the RANDDT (Randomization date). ○ For example of week 2 is missing then ADT = baseline ADT + 2 weeks ● For "APHASE", deciding if the missing row should be marked as "On-Treatment" or "Post-Treatment", the generated ADT should be compared to treatment end date "TRTEDT". If $TRTEDT + 1 \geq ADT$ then "On-Treatment" or if $TRTEDT + 1 < ADT$ then "Post-Treatment". |

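### SAP 10.6.3 labels Hgb rows after an on-treatment death Post-Treatment by date alone, although 7.1.5.1 classes them on-treatment; separately, averaging the 200 imputations makes displayed Hgb SDs slightly too small (both minor)

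*SAP*

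**What the plan says.** **Deaths.** SAP 7.1.4 sets death apart from the other intercurrent events: "For deaths, a hypothetical strategy will be used as described in Section" 7.1.5.1. That section splits missing Hgb into two classes, each imputed only from observed data of the same class. The on-treatment class includes "Patients who die, use non-randomized ESA Medication, Receipt of Blood Transfusions while on treatment"; deaths after treatment discontinuation go to the off-treatment class. It refers to 10.6.3 for the assumptions about missing values.

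SAP 10.6.3 (Imputation, HGB) creates a row for each missed scheduled visit, dates it as baseline plus the nominal number of weeks, and sets the phase variable APHASE from dates alone: "the generated ADT should be compared to treatment end date" (TRTEDT). A row dated later than TRTEDT + 1 is Post-Treatment. Death is not mentioned.

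SAP 10.6.1 defines the treatment stop date: "Calculated as the latest randomized treatment dose stop date". SAP 10.6.2 adds that where "a participant on randomized treatment dies and has a missing treatment stop date", the date of death is used.

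**Displays.** SAP 10.6.3 (Imputed Hemoglobin Values) replaces each missing Hgb in summary tables and figures by the mean of its 200 imputations. SAP 7.1.5.1 has these tables show SD, quartiles and extremes, and repeats them with imputed values included (Tables 2.3 and 2.4, with 2.8 by subgroup). Inference uses Rubin's rules.

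**The concern.** The phase label decides which observed data an imputation draws on. The primary estimand treats death hypothetically, and 7.1.5.1 carries that out by imputing on-treatment deaths from on-treatment data. A programmer who follows 10.6.3 literally would impute the same rows from participants who had stopped treatment, some of whom may have been rescued. Two competent programmers could therefore build different primary datasets from the same plan. SAP 7.2.5.2 reuses the imputed values for the responder endpoint, so both confirmatory Hgb analyses are touched.

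The display point is separate. The mean of 200 imputations has lost its residual scatter. A table that mixes observed values with such means understates the spread of Hgb.

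**Working it through.** **1. Labels under the two rules.** Days are counted from baseline, and TRTEDT is set to the day of death, the latest it can sensibly be.

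| On-treatment death | TRTEDT + 1 | Evaluation-period rows still to be imputed | 10.6.3 | 7.1.5.1 |
|---|---|---|---|---|
| Week 6 | 43 | Week 24 (168), Week 28 (196) | Post | On |
| Week 13 | 92 | Week 24, Week 28 | Post | On |
| Week 21 | 148 | Week 24, Week 28 | Post | On |
| Week 25 | 176 | Week 28 | Post | On |

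The labels differ in every case. An earlier last dose gives the same result. ESA use, transfusion or interruption with dosing continued gets the same label under both rules.

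**2. Where the label changes the imputation.** SAP 7.1.5.1 has a fallback: "If there are no observed off-treatment Hgb values at a visit, the missing Hgb values at that visit will be imputed" from on-treatment values only. At such a visit the label makes no difference. Protocol Table 3, however, schedules off-treatment Hgb at Weeks 4, 16, 24 and 28, at the early treatment discontinuation visit and at unscheduled visits. Both evaluation-period visits can therefore have off-treatment donors.

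**3. Size for the primary endpoint.** The protocol's own figure is reproduced first. With SD 1.5 g/dL and 270 evaluable per arm (Protocol 10.2.1), the smallest significant difference is 1.96 × 1.5 × √(2/270) = 0.253, matching the stated 0.25 g/dL.

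The SAP analyses all randomized participants, so with 300 per arm the SE is 1.5 × √(2/300) = 0.122 g/dL.

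Shift in an arm's mean = share dying on treatment before Week 24 × on/off-treatment gap. The imputation model conditions on prior Hgb, so the relevant gap is the one left after that conditioning. The documents give neither input. Assumed: 1–2% deaths and a gap of 0.3–1.0 g/dL, the upper end equal to the protocol's expected treatment effect.

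- Low: 0.01 × 0.3 = 0.003 g/dL; 0.003/0.122 = 2.5% of the SE.
- High: 0.02 × 1.0 = 0.020 g/dL; 0.020/0.122 = 16% of the SE.

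A wider set (1–5% deaths, gap 0.5–1.5 g/dL) gives 0.005–0.075 g/dL, still well below 0.25. A death between Weeks 24 and 28 has only its later value affected.

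**4. Size for the responder endpoint.** Even if the label changed the responder status of every such participant, an arm's rate could not move by more than the share of deaths: 1–2 percentage points under the same assumption. The protocol's smallest significant difference is 8 points.

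**5. Displayed SD.** With share m missing completely at random and imputation-model fit R²:

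SD ratio = √(1 − m(1 − R²)).

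Take m = 0.10, the protocol's withdrawal ceiling:

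- R² = 0.2: √0.92 = 0.959, so 4.1% too small.
- R² = 0.7: √0.97 = 0.985, so 1.5% too small.

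At m = 0.05 the shortfall is 0.8–2.0%. A simulation with n = 300, 200 imputations, a true SD of 1.5, m = 0.10 and R² = 0.2 gave a displayed SD of 1.441 with averaging and 1.505 with proper imputations; the formula gives 1.5 × 0.959 = 1.439.

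**6. Any CI computed from averaged values.** CI ratio = √(1 − m(1 − R²)) / √(1 + m(1 − R²)/(1 − m)).

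At m = 0.10:

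- R² = 0.2: 0.959/√1.0889 = 0.919, so 8.1% too narrow.
- R² = 0.7: 0.985/√1.0333 = 0.969, so 3.1% too narrow.

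This reaches Figures 2.1 and 2.2 only if they plot these values. Their titles in SAP 10.10.7 say they include imputed data; the text of 7.1.5.1 speaks only of available values.

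**The case against.** **Section 7.1.5.1 governs.** The estimand section names it for deaths, and it has an explicit death rule, whereas 10.6.3 is a general derivation that never mentions death. This largely stands as a reading of intent. It does not remove the need to edit, because 7.1.5.1 itself sends the programmer to 10.6.3 and no order of precedence is stated.

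**The note in 10.4.1.1 protects these rows.** It reads: "If the treatment stop date is missing and the treatment start date is non-missing, then the assessment will be considered to be On-Treatment". That would agree with 7.1.5.1, but only if a stop date were missing and left unfilled. SAP 10.6.1 says the eCRF "does not allow for the possibility of missing or partial dates to be recorded for the dose stop date", and 10.6.2 would insert the date of death. Nothing states whether 10.6.2 overrides the note for Hgb phase, so the note is at best a partial answer.

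**Stronger readings.** A reader might infer three things that the documents do not support.

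- That wrongly labelled rows will certainly enter the primary analysis. This assumes that 10.6.3 prevails, which the SAP does not say.
- That the averaging understates the primary standard error. It does not: inference pools the 200 datasets by Rubin's rules.
- That 7.1.5.1 and 10.6.3 disagree about which data the displays use. SAP 7.1.5.1 explains its phrase as meaning that imputed values are included, which is compatible with 10.6.3 showing their average.

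**The effect is too small to matter.** This stands as to severity. Both parts are minor.

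**Conclusion.** Minor, but wrong as written. For an on-treatment death with a recorded or filled stop date, the two sections give opposite labels to the same rows, and those rows enter the primary and first principal secondary analyses. The likely effect is 0.003–0.020 g/dL on an arm mean, against an SE of 0.122 g/dL and an expected difference of 1.0 g/dL. This rests on assumed death rates and gaps. The direction is unknown, because off-treatment donors may have received rescue. No change to the primary conclusion is expected. The imputation summary required by 7.1.5.1 (Table 2.5) will show the number of deaths by arm, so the actual exposure can be checked.

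The averaging rule certainly shrinks the SDs and quartile spread in Tables 2.3, 2.4 and 2.8; only the amount depends on the assumed missingness and R². Tables 2.1 and 2.2 show observed data and are not affected.

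**What to change.** 1. Add to the APHASE rule in SAP 10.6.3: rows after the death of a participant who had not permanently discontinued randomized treatment before death are set to On-Treatment, as in Section 7.1.5.1; rows after a death that follows discontinuation stay Post-Treatment.

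2. In 10.6.3, replace the averaging sentence for Tables 2.3, 2.4 and 2.8. Compute the summaries within each of the 200 datasets. Combine means and SEs by Rubin's rules and report the SD as the root of the mean within-dataset variance. Give quartiles and extremes from observed data, with a footnote. State which values Figures 2.1 and 2.2 plot, and use the pooled SE for their intervals if imputed values are included.

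The cost is SAP wording and programming, best settled before unblinding. No new data are needed. Displayed SDs, and any intervals built from these values, become slightly larger.
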